8.1.1. Statistical Methods for Binary Variables

For all binary endpoints, a summary of the number of responders based on FAS with OC in each treatment arm at each time point will be produced and the response rate will also be plotted against time, by treatment group. In addition, similar tables and figures will be generated based on FAS with NR imputation for IGA response, EASI50/75/90 and NRS response.

8.1.1.1. Primary Analysis

The primary analysis is the analysis of the primary endpoint, IGA clear (0) or almost clear (1) and ≥ 2 points improvements at Week 12, based on the FAS population. NR approach will be used to handle missing values as described in [Section 7.1](#).

IGA response at Week 12 will be analyzed using the Emax dose-response model. The estimation of E_0 , E_{max} and ED_{50} will be reported in mean, standard deviation and 95% CI. These can be implemented by using PROC NL MIXED in SAS.

The three parameter Emax model is a non-linear equation such that the expected response E with or without baseline disease severity in the model can be written as:

$$E = E_0 + \frac{E_{max} Dose}{ED_{50} + Dose}$$

Where:

E is the logit function for the log odds of response $Logit(p)$.

E_0 is in placebo IGA response.

E_{max} is the difference between maximum achievable response (at infinite dose) and baseline.

ED_{50} is the dose that produces half maximal effect ($E_0 + E_{max}/2$).

The 3-parameter Emax model describes a dose response that starts at E_0 and smoothly increases to an asymptote. The fitted curve will be graphically displayed with 95% confidence band. Model based estimation of treatment effect for each dose compared to placebo will be presented with 95% confidence interval.

Sensitivity analyses for IGA will be performed with generalized linear mixed models (GLMM) on FAS population with OC. Fixed factors include treatment, covariates (baseline disease severity such as EASI score), visit and treatment by visit interaction. Random effect includes random intercept for each subject. These can be implemented with SAS PROC GLIMMIX. P-values and inference for odds ratios between treatments will be provided based on the link function of logit. A delta method will be used to obtain 90% confidence intervals

for the risk differences. The overall p-value for treatment effect at each time point may be also presented. In addition, logistic regression analysis including treatment, covariates (baseline disease severity) at each time point will be performed on FAS with NR missing value imputation.

When an Emax model does not adequately capture the dose-response relationship or the Emax model does not converge, analysis from GLMM on FAS with OC and/or logistic regression on FAS with NR imputation may be considered for decision making to characterize the dose-response with dose being considered as a continuous variable.

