Appendix 12. Example SAS Code for Analyses OF Dose-Response Models

This code has been included as an example to show possible ways of fitting an Emax model and in SAS. The actual code may be adjusted, depending on the testing of programming and the data. No SAP amendment is needed if the actual code is different from the example code in this section. The common procedure of PROC NLMIXED has been used. Therefore, PROC NLMIXED has also been used as the ESTIMATE statement allows you to specify the contrast of interest. As our decision criteria are based on differences in proportions this procedure allows us to back transform and express the data in this format. The following code was written assuming the format of the input dataset is of the form:

DOSE	LNDOSE	COUNT	N
0	-9.2103	5	30
10	2.3025	9	30
303.4012	11	30	
100	4.6052	18	30
200	5.2983	21	30

where

DOSE=DOSE in mg,
LNDOSE=log(DOSE+0.0001)
COUNT=number of responses,
N=number of subjects

/* SAS example code */

*** Model 1: EMAX MODEL without covariate ***;

**Degrees of freedom is number of subjects-number of parameters (3);
proc nlmixed data=resp alpha=0.1 df=&df;

** specify that ed50 must be positive;
bounds ed50>0;

eta = e0 + ((emax*dose)/(ed50+dose));
expeta = exp(eta);
p = expeta/(1+expeta);

model count ~ binomial(n,p);

** LOG(ODDS RATIOS) - TAKE EXP(ESIMATE) and EXP(CI) TO CALCULATE PARAMETER AND 60% CI FOR MAIN BODY TABLE;

** ACTUAL ESTIMATED PROPORTIONS ;

estimate 'Model 1: Actual proportions 200mg'
exp(e0 + (emax*200/(ed50+200)))/(1 + exp(e0_int + (emax*200/(ed50+200))));

estimate 'Model 1: Actual proportions 100mg'

$\exp(e_0 + (e_{max} * 100 / (ed50 + 100))) / (1 + \exp(e_0_int + (e_{max} * 100 / (ed50 + 100))))$;

estimate 'Model 1: Actual proportions 30mg'

$\exp(e_0 + (e_{max} * 30 / (ed50 + 30))) / (1 + \exp(e_0_int + (e_{max} * 30 / (ed50 + 30))))$;

estimate 'Model 1: Actual proportions 10mg'

$\exp(e_0 + (e_{max} * 10 / (ed50 + 10))) / (1 + \exp(e_0_int + (e_{max} * 10 / (ed50 + 10))))$;

estimate 'Model 1: Actual proportions 0mg'

$\exp(e_0) / (1 + \exp(e_0_int))$;

** Differences among ACTUAL ESTIMATED PROPORTIONS ;

estimate 'Model 1: proportion difference 200mg vs. placebo'

$\exp(e_0 + (e_{max} * 200 / (ed50 + 200))) / (1 + \exp(e_0_int + (e_{max} * 200 / (ed50 + 200)))) - \exp(e_0) / (1 + \exp(e_0_int))$;

estimate 'Model 1: proportion difference 100mg vs. placebo'

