$\exp(e_0 + (e_{max} * 100 / (ed50 + 100))) / (1 + \exp(e_0_int + (e_{max} * 100 / (ed50 + 100)))) - \exp(e_0) / (1 + \exp(e_0_int))$;

estimate 'Model 1: proportions difference 30mg vs. placebo'

$\exp(e_0 + (e_{max} * 30 / (ed50 + 30))) / (1 + \exp(e_0_int + (e_{max} * 30 / (ed50 + 30)))) - \exp(e_0) / (1 + \exp(e_0_int))$;

estimate 'Model 1: proportion difference 10mg vs. placebo'

$\exp(e_0 + (e_{max} * 10 / (ed50 + 10))) / (1 + \exp(e_0_int + (e_{max} * 10 / (ed50 + 10)))) - \exp(e_0) / (1 + \exp(e_0_int))$;

ods output AdditionalEstimates=est

FitStatistics=loglike

ParameterEstimates=parms;

run;

Appendix 13. Estimate and Confidence Interval for Risk Difference (Proportion Difference) Using GLIMMIX Procedure with link=logit

It is known that the estimate and CI on the logit scale can be obtained using GLIMMIX procedure with dist=binary and link=logit; and using link option in GLIMMIX will generate the estimate for proportions. The variance of risk difference (proportion difference) cannot be directly obtained by GLIMMIX procedure using link=logit. This appendix describes how to obtain the estimate and the confidence interval (CI) for risk difference (proportion difference) by delta method.

Suppose that p_1 and p_2 are the two proportions of interest. $l_1 = \log \text{it}(p_1) = \log\left(\frac{p_1}{1-p_1}\right)$ and

$l_2 = \log \text{it}(p_2) = \log\left(\frac{p_2}{1-p_2}\right)$ are the logit for the two proportions. Note that the l_1, l_2, p_1

and p_2 can be obtained by GLIMMIX procedure, and so are the covariance matrix for l_1 and l_2 . Our interest is to derive the variance of $p_1 - p_2$.

Denote that $f(l_1, l_2) = \frac{e^{l_1}}{1+e^{l_1}} - \frac{e^{l_2}}{1+e^{l_2}} = p_1 - p_2$. A Taylor series expansion of $f(l_1, l_2)$ about the values (l_{10}, l_{20}) is given by:

$$f(l_1, l_2) = f(l_{10}, l_{20}) + \frac{\partial f(l_1, l_2)}{\partial l_1} \Big|_{(l_{10}, l_{20})} (l_1 - l_{10}) + \frac{\partial f(l_1, l_2)}{\partial l_2} \Big|_{(l_{10}, l_{20})} (l_2 - l_{20}) + (2\text{nd or higher order terms}).$$

Therefore

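### As coded in SAP Appendix 12, the 95% CI for ED50 would be a symmetric interval in mg: its lower limit is a negative dose, and under the design rates it covers about 77–89% if the true ED50 is 10–100 mg

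*SAP*

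**What the plan says.** SAP 8.1.1.1 makes a three-parameter Emax model on the logit scale the primary analysis of Week 12 IGA response. E0, Emax and ED50 "will be reported in mean, standard deviation and 95% CI". On software it adds only this: "These can be implemented by using PROC NL MIXED in SAS". It does not say how the interval is formed or on what scale.

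Appendix 12 gives the one worked implementation. ED50 enters the linear predictor as a parameter in mg. The only protection is a comment, "specify that ed50 must be positive", and the statement "bounds ed50>0". The procedure is called with "proc nlmixed data=resp alpha=0.1 df=&df;", and a comment sets the degrees of freedom to the number of subjects minus three. The parameter results are saved by "ParameterEstimates=parms". The appendix presents the code as an example that may be changed without a SAP amendment.

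**The concern.** By default the limits in that table are the estimate plus or minus a t quantile times the standard error. The positivity bound restricts the estimate but not the interval around it. ED50 is a positive quantity with a right-skewed sampling distribution, and with about 50 binary outcomes per arm its standard error is about as large as the estimate. A symmetric interval then goes below zero at one end and stops too early at the other.

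ED50 is a named output of the primary analysis, and SAP 8.2.2.1 gives characterising the dose response as the aim of that analysis. An upper limit that is too low makes the tested doses appear to have passed the half-maximal point more securely than the data show.

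**Working it through.** **The plan's own figure.** The SAP states no operating characteristic for the ED50 interval. Its design rates can be checked against the stated power of about 95% (SAP 4.2.4). With 10% vs 43%, 50 per arm and one-sided alpha 0.0125 (z = 2.241):

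- Pooled term: √(2 × 0.265 × 0.735) = 0.624. Unpooled term: √(0.10 × 0.90 + 0.43 × 0.57) = 0.579.
- (0.33 × √50 − 2.241 × 0.624) / 0.579 = 1.61, so power is 94.7%.

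The stated power reproduces at 50 per arm, one-sided. At 40 per arm it is 88.3%.

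**The SAP's example data.** Appendix 12 lists 5, 9, 11, 18 and 21 responders of 30 at 0, 10, 30, 100 and 200 mg. Maximum likelihood gives E0 = −1.488, Emax = 2.953 and ED50 = 55.3 mg with SE 62.7. With 150 − 3 = 147 degrees of freedom, t = 1.976 for 95%.

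- In mg, 95%: 55.3 ± 1.976 × 62.7 = −68.6 to 179.1 mg.
- In mg, at the code's alpha of 0.1 (90%): −48.5 to 159.0 mg.
- Log scale, 95%: the SE of log ED50 is 62.7 / 55.3 = 1.134, and exp(1.976 × 1.134) = 9.4. The limits are 55.3 / 9.4 = 5.9 mg and 55.3 × 9.4 = 520 mg.
- Profile likelihood, 95%: 8.1 mg upward, with no finite upper limit found up to 1,000,000 mg.

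A natural-scale lower limit is negative whenever SE / estimate exceeds 1 / t, about 0.51. Here the ratio is 1.13.

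**Simulation under the design rates.** Inputs from the documents are the doses, 10% on placebo, 43% at 200 mg and 250 randomised. Discontinuations count as non-responders (SAP 7.1), so about 50 per arm enter the fit. Two inputs are assumptions: equal allocation to the five arms, and the true ED50, which was varied. For each ED50, E0 = logit(0.10) and Emax = [logit(0.43) − logit(0.10)] × (ED50 + 200) / 200. There were 1,000 trials per row. Results are for fits with an interior estimate and a nominal 95% level.

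| True ED50 (mg) | No interior estimate | Lower limit < 0 | Coverage, mg scale | Coverage, log scale | Coverage, profile |
|---|---|---|---|---|---|
| 10 | 1.4% | 99.8% | 87.1% | 99.5% | 95.1% |
| 30 | 2.8% | 99.9% | 82.3% | 95.2% | 93.9% |
| 60 | 5.8% | 100% | 79.5% | 93.7% | 96.4% |
| 100 | 10.7% | 100% | 78.1% | 92.3% | 96.2% |
| 200 | 20.9% | 100% | 70.8% | 88.5% | 95.6% |

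Monte Carlo error is about 1.2 points (at ED50 30: √(0.823 × 0.177 / 972)). Every miss in mg has the upper limit below the true ED50. Separately coded simulations put coverage for 10–100 mg between 77% and 89%. Median SE / estimate was 0.94 at ED50 30 and 1.16 at ED50 100, both well above 0.51.

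**Sensitivity.**

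- True ED50 of 5 mg: coverage is 94.5%, and the lower limit is still negative in all interior fits.
- 40 per arm: coverage is 87.2, 81.2, 78.8, 73.9 and 70.1% for ED50 10, 30, 60, 100 and 200.
- Fits that run off to a very large ED50 counted as covering: at ED50 200, (0.708 × 791 + 209) / 1,000 = 77%.
- Code's 90% level: the lower limit is negative in 96.6–99.8% of interior fits for ED50 10–200.
- Larger effect than planned (5% to 60%): the lower limit is negative in 77.6% (ED50 10) and 92.8% (ED50 30). Coverage is 88.6% and 86.4% in mg, and 92.4% and 92.8% by profile likelihood.

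**The case against.** The strongest reply is that the SAP text does not prescribe this interval. The quoted sentence names no method, and the Wald form is inferred from example code that may be changed freely. That code cannot be the literal source of a 95% interval, because it sets a 90% level. One of its comments mentions a 60% interval, and its estimate lines use a term, `e0_int`, that the model never defines. This stands, and the point is limited to what the code would produce. It does not remove the gap: no other method is prespecified, and the default in the only code shown gives negative doses.

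A reader might infer that coverage is 77–89% whatever the truth, or that every trial would give a negative limit. The documents support neither. The true ED50 is not stated, and a response larger than planned leaves some lower limits positive.

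A reader might also infer that the trial's conclusions are at risk. They are not. The hypotheses in SAP 4.1 concern response against placebo, Appendix 12 ties the decision criteria to differences in proportions, and 8.1.1.1 gives each dose effect its own interval. No rule uses the ED50 interval. The SAP also has fallbacks when the Emax model does not fit or converge, so some of the fits without an interior estimate might not report an ED50 at all.

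Finally, the EASI Emax model in 8.1.2 might seem to share the defect. That section does not itself promise an ED50 interval, and no continuous-endpoint check was made, so the point does not extend there.

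**Conclusion.** The concern holds for the code as shown. If Appendix 12 is run with its level changed to 95%, the ED50 interval is −68.6 to 179.1 mg on the SAP's example data, a result that needs no assumed ED50. Under the design rates with about 50 per arm and a true ED50 of 10–100 mg, the lower limit is negative in essentially every interior fit and coverage is about 77–89%, with all misses at the top. The size of the shortfall rests on the assumed ED50: almost none at 5 mg, and about 24 points (95 − 71) at 200 mg among converged fits. The consequence is a wrong error bar on a descriptive but named primary-analysis parameter. It should be corrected before unblinding, but it does not affect the efficacy inference.

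**What to change.** In SAP 8.1.1.1, state that the 95% interval for ED50 is a profile-likelihood interval. Add that an upper limit that is not finite is reported as unbounded, and say what is reported when the fit has no interior estimate.

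In Appendix 12, add the profile step and change alpha from 0.1 to 0.05 so that the code matches the stated 95%.

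A simpler option is to estimate log ED50, replacing ED50 in the predictor by its exponential, and to exponentiate the limits. This keeps both limits positive but is only approximately calibrated: 99.5% at ED50 10 mg down to 88.5% at 200 mg, against 93.9–96.4% for profile likelihood over the same range. Its 520 mg limit on the example data is finite where the profile limit is not.

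The cost is a sentence or two in the SAP, a few lines of code, and a wider, sometimes unbounded, upper limit. The ED50 point estimate and the dose-versus-placebo estimates do not change.

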8.1.1.2. Other Analysis of Binary Data

The analyses for other binary endpoints will be performed using GLMM on the FAS population with OC as described in [Section 8.1.1.1](#). Logistic regression analysis may be performed on FAS with NR imputation in case of convergence issues from GLMM.

8.1.1.3. Safety Data

An unconditional exact method for risk difference proposed by Chan and Zhang (1999) will be used to compare each active dose to placebo. P-values and 90% confidence intervals will be formed for tier 1 events and 90% confidence intervals will be formed for tier 2 events.

The exposure adjusted summaries for the Tier 1 and Tier 2 events will also be conducted. See [Section 8.2.1](#) for the calculation of exposure.

8.1.2. Statistical Methods for Continuous Variables

Unless stated otherwise, descriptive summary statistics for continuous variables will be presented on FAS with OC by treatment group and will include the following: n, mean, median, standard deviation, minimum and maximum. In addition, similar tables will be generated on FAS with LOCF imputation for EASI, NRS, SCORAD scores and BSA. For longitudinal continuous variables, such as the percent changes from baseline of EASI score, percent changes from baseline of pruritus NRS score etc., the primary analysis will be conducted using a mixed model repeated measures (MMRM) analysis on FAS with OC. Each analysis will be performed with a restricted maximum likelihood (REML) MMRM analysis. The model will include treatment and visit as fixed factors, along with the interaction of treatment and visit. Baseline measurement such as baseline disease severity will be used as a covariate. An unstructured covariance structure will be used to model the within-subject variability. In the event there are difficulties with initially fitting an unstructured covariance matrix, a variety of methods will be used to facilitate the computations. The Kenward-Roger approximation will be used to estimate the denominator degrees of freedom. The model will be fit using SAS PROC MIXED. Least squares (LS) means of the treatment groups at each available visit along with 90% CIs will be presented. LS mean difference between treatment and placebo for each visit will be presented along with 90% confidence intervals. Least squares means and confidence intervals will be back transformed to an appropriate scale when necessary. In addition, ANCOVA including treatment and baseline disease severity on FAS with LOCF imputation will be performed.

For the key secondary endpoint (percent change of EASI score from baseline to Week 12), a dose-response relationship will be characterized by a three-parameter Emax model described in Section 8.1.1.1, in which case E denotes the percent change of EASI at Week12 and E₀ denotes the percent change of EASI at Week12 in placebo group.

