9.2.2. Analysis of the Secondary Endpoints

The key secondary endpoint is the percent change from baseline in EASI score at Week 12. The treatment effect in each of the active treatment groups is the difference (mean percent change from baseline at Week 12 in the active treatment group minus the mean percent change from baseline at Week 12 in the placebo group) in the mean percent change from baseline of a EASI score at Week 12.

The estimates for treatment effect will be obtained by fitting the mixed-effect models repeated measures (MMRM) assuming missing at random to the percent change of EASI score from baseline score if there is no convergence issue. The model will include time, treatment (active doses and placebo), treatment by time interaction as fixed effects and baseline value as a covariate. We will allow an unstructured variance-covariance matrix. Covariance matrices with other structure will be considered in sensitivity analysis. Estimates and the appropriate confidence intervals will be presented.

In addition to the primary analysis based on the pairwise evaluation of the treatment effects, we will explore the modeling of dose-response relationship for the key secondary endpoint.

MMRM will also be employed for other continuous endpoints such as percent change from baseline in the EASI total score at all scheduled time points, percent change from baseline in the pruritus NRS from baseline at all scheduled time points, change from baseline in affected BSA at all scheduled time points, and change from baseline in SCORAD at all scheduled time points. Estimates of mean values and the mean differences from placebo at each week

(along with 90% confidence intervals) will be reported. Descriptive statistics of the actual and change from baseline values will be calculated.

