4.2.2. Multiplicity Adjustment

The multiplicity adjustments are considered only in the analysis of the primary endpoint when the Emax model does not fit. Hochberg method (Hochberg, 1988) is used to account for that the null hypothesis will be rejected if a treatment effect is detected at Week 12. The overall Type I family-wise error rate (FWER) is controlled at 0.05 (one-sided).

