4.2.4. Efficacy Analysis and Sample Size Justification

The sample size is based on the primary efficacy endpoint, IGA response rate of clear or almost clear and ≥ 2 points improvement at Week 12. For IGA response rate at Week 12, a total of 250 randomized subjects in the 5 treatment groups (providing approximately 200 completers, 40 completers per treatment group assuming 20% dropout rate) will provide approximately 95% power to detect a 33% difference between PF-04965842 and placebo assuming placebo response rate is approximately 10%, and significance level is 0.0125 (Bonferroni adjusted with 4 comparisons).

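### The MMRMs fit one baseline slope to all visits from Week 1 to Week 16; if the baseline relationship changes over time, the Week 12 contrast loses precision that a baseline-by-visit term would recover almost free

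*SAP*

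**What the plan says.** On the fixed effects, SAP 8.1.2 states: "The model will include treatment and visit as fixed factors, along with the interaction of treatment and visit". On baseline it adds: "Baseline measurement such as baseline disease severity will be used as a covariate". Protocol 9.2.2 describes the same model for the key secondary endpoint, ending with "treatment by time interaction as fixed effects and baseline value as a covariate". SAP 6.3 also treats baseline only as a covariate. The rest of SAP 8.1.2 is detailed (REML, unstructured covariance, Kenward-Roger degrees of freedom, the SAS procedure), so a programmer following it would fit a single baseline coefficient.

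This model is the main approach for percent change in EASI (key secondary), percent change in pruritus NRS, change in BSA, change and percent change in SCORAD, and change in NRS, DLQI, POEM and HADS (SAP 8.2.2.2.1, 8.2.2.4 and 8.2.5). The table in SAP 8.2.5 marks follow-up as included for all of them, so the one slope also covers the off-treatment visits. Neither document gives a reason for holding the slope constant.

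**The concern.** A single slope assumes that baseline predicts the outcome equally well one week into treatment, at Week 12, and four weeks after stopping. For a change score this is doubtful. Early scores usually still track baseline, while later ones track it less, so the slope of change on baseline drifts from near 0 towards -1.

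With an unstructured covariance, the fitted slope weights visits by their residual precision given baseline. It need not be close to the Week 12 slope. Where it differs, baseline variation that should have been removed from the Week 12 comparison stays in as noise. At stake is the width of the Week 12 intervals for the key secondary endpoint and the other continuous endpoints.

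**Working it through.** **1. The plan's own figure.** The only sizing calculation is for the IGA endpoint. SAP 4.2.4 states "a total of 250 randomized subjects in the 5 treatment groups", with "40 completers per treatment group assuming 20% dropout rate", which "will provide approximately 95% power to detect a 33% difference between PF-04965842 and placebo assuming placebo response rate is approximately 10" percent; the "significance level is 0.0125 (Bonferroni adjusted with 4 comparisons"). SAP 4.2.2 supplies the sidedness: "The overall Type I family-wise error rate (FWER) is controlled at 0.05 (one-sided"), and 0.05/4 = 0.0125.
- Rates are 0.10 and 0.43, pooled 0.265, with 50 per arm.
- Null SE = √(2 × 0.265 × 0.735/50) = 0.0883. Alternative SE = √((0.10 × 0.90 + 0.43 × 0.57)/50) = 0.0819. Critical z = 2.241.
- (0.33 − 2.241 × 0.0883)/0.0819 = 1.61, so power is 94.7%.

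The stated figure reproduces with 50 analysed per arm; with 40 it is 88.3%. It supplies no SD or correlation for any MMRM endpoint, so everything below uses assumed values.

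**2. Visits.** The Schedule of Activities has EASI, BSA and SCORAD at Weeks 1, 2, 4, 6, 8, 12, 13, 14 and 16: nine post-baseline visits. A slope per visit therefore adds 8 parameters, and fewer for the patient-reported outcomes, which skip Week 13.

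**3. Formula.** Let b be the vector of visit-specific slopes on baseline, S the residual covariance given baseline, and sB the baseline SD. With a full treatment-by-visit mean and unstructured covariance, the common slope is

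g = (1′S⁻¹b)/(1′S⁻¹1).

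The Week 12 contrast variance is proportional to s12² + (b12 − g)²sB², against s12² with a slope per visit. Hence

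information lost = (b12 − g)²sB² / [s12² + (b12 − g)²sB²].

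**4. Change scores, equal SDs (sB = 1).** Assume that the correlation between two occasions d weeks apart is a + (c − a)e^(−kd), so b_t = ρ_t − 1, where ρ_t is the correlation of week t with baseline.
- c = 0.9, a = 0.2, k = 0.1: ρ is 0.83 at Week 1 and 0.41 at Week 12. Week 1 has weight 0.50 in g and Week 12 has 0.03. g = −0.29 and b12 = −0.59, so (b12 − g)² = 0.089. s12² = 1 − 0.41² = 0.831. Loss = 0.089/0.920 = 9.7%.
- c = 0.95, a = 0, k = 0.1: g = −0.288, b12 = −0.714, s12² = 0.918. Loss = 0.181/1.099 = 16.5%.
- c = 0.9, a = 0.6, k = 0.05: loss 1.8%.
- Same correlation with baseline at every visit: loss 0.

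Over the grid c = 0.80 to 0.95, a = 0 to 0.6, k = 0.02 to 0.2, the loss runs from 0.1% to 16.5%. Week 1 carries weight 0.20 to 0.63 and Week 12 carries 0.01 to 0.07. Simulation with 5 arms of 40 and complete data gave 8.8%, 14.9%, 1.7% and about 0 for the four cases above.

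**5. Other assumed patterns.**
- SD constant or rising 30%, residual correlation 0.5 to 0.7 per root-week. If the correlation with baseline falls from 0.85 to 0.30, Week 12 variance rises 10% to 29% (information lost 0.10/1.10 = 9% to 0.29/1.29 = 22%). For 0.80 to 0.40 it rises 4% to 13%, and for 0.75 to 0.50, 0% to 4%.
- Week 1 residual variance far smaller than the rest: Week 1 weight about 1.0 to 1.25, loss 5% to 22%.
- Spread shrinking with improvement: the change-score loss reached 28% at 40% mean improvement, while at 70% improvement the Week 1 weight fell to 0.05 to 0.25.
- Percent change in EASI: 0% to 15% overall, 1% to 6% at 40% mean improvement, and below 0.3% at 70%.

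**6. Translation.** A 15% loss makes 40 completers act like 40 × 0.85 = 34 and widens the interval by 1/√0.85 − 1 = 8%. A 28% loss gives 40 × 0.72 = 29 and 18%.

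**7. Cost of a slope per visit.** Estimating one slope costs about 1/n of the Week 12 variance: 1/250 = 0.4% and 1/200 = 0.5%.

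**The case against.** A common-slope MMRM is a valid analysis, and the documents contain nothing that shows a loss in this trial. The drift from 0 towards -1 describes absolute change. The key secondary endpoint is a percent change, and if the expected score is proportional to baseline, percent change has zero slope at every visit and nothing is lost. Formal inference and multiplicity control concern IGA response only (SAP 4.1, 4.2.2), and no decision rule or sample size rests on an MMRM interval. Week 12 EASI also has an Emax model and an ANCOVA.

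Most of this stands, and it limits the size and weight of the point. The ANCOVA is not a substitute, because it is a sensitivity analysis on LOCF data.

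Three stronger readings are tempting, and the documents do not support them:
- *The Week 12 comparison is adjusted with the Week 1 slope and wastes about a fifth of the information in every MMRM.* Setting g to the Week 1 slope with correlations 0.8 and 0.3 does give 0.25/(0.91 + 0.25) = 21.6%. But g is an average whose Week 1 weight ranged from 0.05 to above 1 depending on the assumed covariance, and a fifth is too high for percent change in EASI.
- *The misfit biases the treatment effect.* With complete data, randomisation keeps the contrast unbiased and the unstructured covariance absorbs the misfit. Bias in the contrast needs baseline-dependent dropout that differs by arm. A deliberately adverse simulation (18% to 20% dropout, placebo losing severe and active losing mild patients, correlation 0.85 to 0.30) gave a false Week 12 difference of 0.05 to 0.13 residual SD. Nothing in the documents predicts that pattern.
- *The primary result is affected.* The IGA analysis does not use this model.

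**Conclusion.** The point holds as a conditional loss of precision. As written, both documents fit one baseline slope over Weeks 1 to 16, and Week 12 often has little say in it. The loss rests entirely on assumed SDs and correlations. It is about 0% to 28% of the Week 12 information for change-from-baseline endpoints (BSA, SCORAD, NRS, DLQI, POEM, HADS), and about 0% to 15%, often a few percent, for percent change in EASI. It is zero if the slope is constant. This is a worthwhile improvement to secondary analyses, not an error that invalidates them: the restriction saves at most about half a percent of variance and may cost far more.

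**What to change.** In SAP 8.1.2 and Protocol 9.2.2, specify every MMRM with treatment, visit, treatment-by-visit, baseline and baseline-by-visit. SAP 6.3 should refer to the same specification.

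The cost is one model term and up to 8 extra slopes, or about 0.4% to 0.5% of Week 12 variance. If the slope is in fact constant, that is a very small net loss. No further data, visits or subjects are needed.
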